Gender and Minority Inclusion: Any participant who meets study criteria and agrees to participate will be included. We will not exclude participants based on ethnicity, but because we do not have standardized translations of the standardized testing instruments, we will restrict inclusion to children for whom English is the primary language. The ratio of males to females with ASD in California is 4.6:1, and we expect that our sample will reflect this ratio.

Participation of Children: Interventions to target attention and eye movement problems in ASD (our long-range goal from this feasibility study) are likely to be more effective in children than adults. The goal of this study is to test whether our portable eye-tracking system is easy and durable for children's use at home, and whether the video games are interesting enough to motivate children's compliance for almost daily use over an extended period. This research falls under section 404 of 45CFR 46 Subpart D ("Research not involving greater than minimal risk").

There are 3 phases of study participation: an initial assessment/orientation, an 8-week intervention training phase, and a final evaluation phase.

Assessment/Orientation Phase: Each participant will come to our lab for two sessions that will take place on separate days. Session 1 will include consent and overall instructions, IQ testing (WASI) ⁹, SRS ¹⁰, and baseline measures of attention and eye movement (Spatial Attention Task, Gap-Overlap and Anti-Saccade Eye Movement Tasks). Session 2 will establish baseline measures on the Simulation Task and Social Interaction Task, and will cover the introduction and trial use of the Training System and instructions for home use. Following this initial assessment, scores on the Spatial Attention and Eye Movement tasks will be used to assign children to one of two intervention groups so that the mean and range of those scores are equivalent between groups. During the intervention phase, Group 1 will receive the gaze-contingent training principles game. Group 2 will play the same game as Group 1 in daily training, except that instead of using gaze, the game play will be joystick-driven.

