Intervention Phase: During this 8-week period, study participants will be asked to play a video game at home for a minimum of 30 minutes per day, 5 times per week. Parents/caregivers will oversee the daily in-home training and will be briefed along with the subjects at Session 2. Participants (and parents) will be phoned during the first 3 days of in-home testing to assure that there are no problems with equipment or use of equipment. Participants will return to our lab at 4 weeks, for an abbreviated round of tests (Level 1, to assess attention and eye movement, described below). Game play will be monitored as in our pilot testing using a secure 'dropbox' through which we will receive daily summaries of the amount of time each child has played the games, amount of time spent in calibration, and notes from the child regarding any problems or comments they might have about the games. If we find that a child is not playing the required amount of time, or has excessive calibration time, we will contact the family and follow-up with a home visit to assess the problem if necessary. This system worked very well for us in the pilot testing. Children who withdraw (or whose participation is terminated for failure to play the games) from the study will be replaced. An investigator from the project will always be available to troubleshoot any hardware/software problems, and discuss the child's progress by phone, e-mail, or in-home visits as required.

Final Evaluation Phase At the 8 week lab visit (the end of the intervention period), we will collect postintervention assessment at three outcome levels (direct testing of attention and eye movement and social questionnaires; simulation task testing; real social interaction-- all described below). We will ask trainees and their parents to complete a questionnaire evaluating their experience with particular focus on the ease of use of the equipment and game and the enjoyability of the training game.

Attention/Eye Movement Tests: The following tasks are a direct test of improvement of spatial attention disengagement and orienting and eye movement accuracy and initiation speed.

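### The ease-of-use and enjoyability questionnaire is planned only at week 8, with no provision for children who stop early and are replaced, so its ratings would come from finishers and are likely to be too favourable

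*Combined protocol and SAP*

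**What the plan says.** Under Participation of Children the protocol gives a feasibility purpose: "The goal of this study is to test whether our portable eye-tracking system is easy and durable for children's use at home". The same sentence adds whether the games hold children's interest well enough for near-daily play.

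The instrument for ease of use and enjoyment appears once, in the Final Evaluation Phase: "We will ask trainees and their parents to complete a questionnaire evaluating their experience with particular focus on the ease of use". The timing of that phase is explicit: "At the 8 week lab visit (the end of the intervention period), we will collect postintervention assessment at three outcome levels". The only lab visit during training has a narrower content: "Participants will return to our lab at 4 weeks, for an abbreviated round of tests (Level 1, to assess attention and eye movement". No experience questionnaire is listed there.

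On early stopping, the Intervention Phase says: "Children who withdraw (or whose participation is terminated for failure to play the games) from the study will be replaced". It describes no exit visit or exit form.

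The same section sets up continuous monitoring. Through the dropbox the team receives "daily summaries of the amount of time each child has played the games, amount of time spent in calibration", together with "notes from the child regarding any problems or comments they might have about the games". Families are phoned during the first 3 days. If a child plays too little or spends too long in calibration, "we will contact the family and follow-up with a home visit to assess the problem if necessary". The replacement paragraph just before Gender and Minority Inclusion adds that, if more than two participants fail to complete more than four weeks of training, the user experience will be improved using participant feedback and new participants recruited.

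The Statistical Plan contains no analysis of the questionnaire, play time, withdrawals or replacements.

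**The concern.** A child who finds the eye tracker awkward or the games dull is likely to play less. Playing too little is itself a ground for ending participation. That child leaves before week 8, and the replacement child and parent complete the form instead. Loss from the questionnaire is therefore plausibly related to what the questionnaire measures, and the likely direction is favourable to the system.

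At stake is the structured evidence on whether families find the home system easy and enjoyable. This is a question of which data are collected after a child stops. It does not touch the efficacy analyses.

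**Working it through.** **What each source covers for a child who stops before week 8**

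| Source | Covers early stoppers? | Gives ratings? | Parent's view? |
|---|---|---|---|
| Play time and calibration time | Yes, until stopping | No | No |
| Child's notes | Yes, until stopping | No, free comments | No |
| Calls, family contact, home visits | Yes | No instrument named | Informal only |
| Week-4 visit | If still enrolled | No, Level 1 tests only | No |
| Questionnaire | Not as written | Yes | Yes |

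Only the last row gives structured ratings from child and parent, and it is the row that early stoppers miss.

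**Size of the gap**

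The documents give no rating, rating scale or home-training loss rate, so there is no figure of the plan's own to reproduce. The calculation below is an illustration.

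Inputs:
- Finishers F = 40 (two groups of 20, from the aims), assuming replacement continues until 40 finish.
- Loss d = 10% to 15%. This is an assumption. The protocol gives the figure as an upper expectation for failure to complete in-lab testing, not for home training.
- Proportion of finishers rating the system favourably s = 80% (assumed), with 90% as a check.
- Proportion of leavers who would rate it favourably q = 0% to 50% (assumed).

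Step 1, number who start: N = F / (1 − d), rounded up.
- d = 10%: 40 / 0.90 = 44.4, so 45 start and 5 are unrated (5/45 = 11%).
- d = 15%: 40 / 0.85 = 47.1, so 48 start and 8 are unrated (8/48 = 17%).

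Step 2, favourable percentage among all who start: [40s + (N − 40)q] / N. The overstatement is s minus this, which equals [(N − 40)/N] × (s − q).

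| N | s | q | All starters | Overstatement |
|---|---|---|---|---|
| 45 | 80% | 50% | 34.5/45 = 76.7% | 3.3 points |
| 45 | 80% | 0% | 32/45 = 71.1% | 8.9 points |
| 48 | 80% | 50% | 36/48 = 75.0% | 5.0 points |
| 48 | 80% | 0% | 32/48 = 66.7% | 13.3 points |

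With s = 90%, the same formula gives 4.4 points (N = 45, q = 50%) to 15.0 points (N = 48, q = 0%).

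**The case against.** The strongest reply is that feasibility does not rest on the questionnaire. Compliance is measured directly, each day, for every child. Calibration time and equipment problems bear on ease of use. A child heading for termination is exactly the child whom the calls and home visits are aimed at, and the rule on early stopping foresees acting on participant feedback. All of this stands. A reader might infer that the whole feasibility answer comes from children who finish, and the documents do not support that. What the monitoring lacks is a rating and a structured parent view. The early-stopping rule relies on participant feedback but names no instrument to collect it from those who stopped.

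A reader might also infer that a gaze-versus-joystick comparison of user experience will be biased. The Statistical Plan contains no such comparison, and the documents do not say that leaving differs by device.

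Silence does not forbid an exit form, so it would be too strong to say that leavers can never rate the system. The point is that staff following the text would give the form at week 8 only.

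The direction of bias is likely rather than certain. Reasons for leaving are not stated, and some may have nothing to do with the system. If leavers would rate it as finishers do (q = s), the overstatement is zero.

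Two points on importance also stand. The numbered aims concern conducting the training and evaluating efficacy, and the questionnaire is in neither. With 32 of 40 favourable, the 95% sampling error is about 1.96 × √(0.8 × 0.2 / 40) = 12 points either way, about the size of the largest gap above. Sampling error has no preferred direction, however, whereas selection by failure to play probably does.

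**Conclusion.** The concern holds in a limited form. As written, the structured child and parent ratings of ease and enjoyment would come from finishers only, and they are likely to be too favourable. Under the stated assumptions, 5-8 of 45-48 starters would be unrated and the favourable percentage overstated by about 3-13 points. The loss rate is borrowed from in-lab testing and the ratings are assumed, so this is a range and not a finding. The text on timing and replacement is clear; the size is uncertain. The point affects a stated goal of the pilot and is worth correcting, but it does not affect the efficacy analyses.

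**What to change.** In the Final Evaluation Phase and Intervention Phase, state that the same child and parent questionnaire is given at week 8 or at withdrawal or termination, whichever comes first, by phone, e-mail or home visit, with one added item on the reason for stopping.

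Add a reporting sentence to the Statistical Plan: ratings are shown together with play time and stopping, by group, for all children who start, including those replaced. Leavers are shown separately, and the number who did not answer is stated.

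The cost is small: a sentence or two and, under the assumptions above, forms for 5-8 families. Staff already phone, e-mail and visit these homes. Some leavers will not respond, so the gap will narrow but may not close, and the reported ratings may look less favourable.

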Spatial Attention Task (E-Task): This task is patterned after Posner's classic cued spatial attention tasks, but uses target discrimination rather than detection. The task display is a central fixation cross on a computer monitor flanked by boxes on the left and right. Trials begin with either an attention directing cue (one of the boxes brightened) or a null cue (no change or both boxes brightened). Following a short (100 ms) or long (800 ms)

delay, a target (letter "E" pointing up, down, left or right) is presented in either the cued (valid) or the opposite uncued (invalid) location. The subject moves a joystick lever to indicate target orientation (up, down, left, right). Results from a number of studies using this task demonstrate slowed disengagement and shifting of attention in ASD children and adults. A study that used this task to examine spatial attention development in typically functioning children and adults will provide estimates of typical behavior on this task.

Analysis: Measures to be used from this task are: attention disengagement index (difference between accuracy to cued and uncued targets); attention orienting index (difference between cued targets with short vs. long attention orienting delays)³. Analyses for pilot testing to assess improvement in attentional skills will test the disengagement and orienting indices to: 1) compare individual participants against control performance (using means and variability from age-matched typical controls at pre- and post-testing ⁸. Simple analyses will use a t-test or repeated measures ANOVA to examine attention differences in pre- and post- measures and group differences and interactions.

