From these analyses, it is possible to determine the degree to which participants respond appropriately, both linguistically and behaviorally to social interactive cues. We will examine both speech and non-verbal indications of engagement, such as gaze and gestures. This high level outcome measure allows us to examine the subtleties of social engagement during a conversation. We expect that post-intervention improved attention and eye movement will promote more effective social interaction.

Statistical Plan

All outcome testing will be done before training then repeated after training completion.

Level 1 (and Screening for entry criteria): The first level will use tests we have developed and published to directly test whether the speed, accuracy, and spatial breadth of eye movements and attention have improved. These tasks will be used to screen participants for presence of attention and eye movement deficits and will be used as a direct test of improvement of spatial attention disengagement and shifting and eye movement accuracy and initiation speed.

Measures to be analyzed (indices of attention orienting and disengagement, saccade accuracy, latency and gaze/attention) disengagement are described above as are analyses to evaluate effects at the single case level. Analyses will evaluate treatment outcome and differences in outcome between the two groups. A multivariate analysis (MANOVA) will provide a global (linear vector) comparison of all outcome measures at preand post-testing points for the two groups (i.e., differences in all measures between pre- and post-testing and between groups). Repeated measures ANOVAs for each of the five outcome measures will test improvement over time (slope > 0) and trends (linear, non-linear), and differences between groups in these effects. Level 2: The second level will use a driving simulation to test how well the trainee can negotiate a simulated environment with a variety of obstacles (i.e., test improvement in attentional and visual monitoring and speed and accuracy of response).

Simple analyses will compare (repeated measures ANOVA to examine differences in pre- and post-measures and group differences and interactions).

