Standard analyses will compare number and timing of instances of orienting to or disengaging from a directed social stimulus (repeated measures ANOVA comparing pre- and post-training measures and groups and interactions). More advance analysis will use methods developed by [name]. Linguistic and Nonverbal communicative behaviors will be annotated into the Eudico Linguistic Annotator (ELAN) (Brugman, H., & Russel, A., 2004; Crasborn, O., & Sloetjes, H., 2008). ELAN, a video interface integrates behavioral data at millisecond resolution across multiple channels such as speech, eye gaze, head movement and facial expression. Behavioral states and discreet behaviors can be coded vielding frequency counts, total duration and mean duration as well as the coordination across channels, e.g., integrating an eye gaze shift in response to a question. Drs. [name] and [name] have developed methods for coding social behaviors in typical and atypical children and adults. These analyses include following behavioral categories: (i) Gaze: Location (target), Duration, Frequency; (ii) Head: position and movement; (iii) Speech (transcribed using CHILDES): utterances (content and length) and pauses. From these analyses, it is possible to determine the degree to which participants respond appropriately, both linguistically and behaviorally to social interactive cues. Novel analyses developed by [name] (a consultant on this project) use a recurrence technique in which the level of engagement of the participants is revealed in the pattern of their exchange (Figure 4). We will examine both speech and non-verbal indications of engagement, such as gaze and gestures. We will also obtain SRS scores to compare aspects of social engagement with a standardized assessment. This high level outcome measure allows us to examine the subtleties of visual and spoken engagement during a conversation. We expect that our intervention would promote more effective social interaction.

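### No planned group comparison uses baseline as a covariate; with 20 per group this costs power when the pre-post correlation is low to moderate

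*Combined protocol and SAP*

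**What the plan says.** **Baselines.** Under Assessment/Orientation Phase, the Level 1 tasks and the SRS are measured in Session 1, and "Session 2 will establish baseline measures on the Simulation Task and Social Interaction Task". Every outcome level therefore has a pre-training value.

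**Assignment.** In the same section, "scores on the Spatial Attention and Eye Movement tasks will be used to assign children to one of two intervention groups". The stated purpose of this step is balance: children are placed "so that the mean and range of those scores are equivalent between groups". Random allocation is not mentioned.

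**Group comparisons.**
- Spatial Attention Task and Simulation Task: "Simple analyses will use a t-test or repeated measures ANOVA to examine attention differences in pre- and post- measures and group differences and interactions". The Gap-Overlap and Anti-Saccade paragraphs differ only in referring to eye movement.
- Statistical Plan, Level 1: "A multivariate analysis (MANOVA) will provide a global (linear vector) comparison of all outcome measures" at the pre and post points. Repeated measures ANOVAs of the five measures "will test improvement over time (slope > 0) and trends (linear, non-linear), and differences between groups in these effects".
- Statistical Plan, Level 2: "repeated measures ANOVA to examine differences in pre- and post-measures and group differences and interactions".
- Social Interaction Task and Statistical Plan, Level 3: "repeated measures ANOVA comparing pre- and post-training measures and groups and interactions".

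Baseline appears in these analyses only as one of the repeated values of the outcome. No covariate is named anywhere, including in the more advanced Level 3 methods. No sample-size or power calculation is given.

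**The concern.** Aim 2 is to evaluate efficacy, and the trial has only two groups of 20, so the choice of test matters. A repeated measures ANOVA does use baseline, but only by subtraction. When pre and post values are weakly correlated, subtraction adds noise. An adjusted analysis estimates how much of the baseline to remove.

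Two features of the plan sharpen the point. First, the t-test option in the task sections is not defined. If it means post-training values alone, baseline is not used at all. Second, the groups are balanced on Level 1 scores that then do not enter the model, so the change test's standard error ignores the balance and the test becomes conservative.

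At stake is a higher chance of missing a real group difference than the same data would allow. The validity of the test is not in question.

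**Working it through.** The plan states no power figure to reproduce.

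**Inputs.** From the documents: 20 per group (Aim 1), and testing at 0 and 8 weeks, with a Level 1 visit at 4 weeks. Assumed, because not stated: two-sided 5% level; effect *d* of 0.8 or 0.5 baseline SD; pre-post correlation ρ of 0.3, 0.5, 0.7 or 0.8; post SD equal to *k* baseline SDs, with *k* = 1 or 1.25.

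**Step 1: what the planned test is.** With two time points, group-by-time is a t-test on post minus pre. With 0, 4 and 8 weeks, the linear-trend weights are −1, 0, +1, which is again post minus pre.

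**Step 2: variance per child, in baseline SD².**
- Change: 1 + k² − 2ρk, 38 df
- Post only: k², 38 df
- ANCOVA: k²(1 − ρ²), 37 df, times a mean factor of 1 + 1/36 = 1.028 for estimating the slope

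For k = 1, the ANCOVA/change ratio before that factor is (1 − ρ²)/(2 − 2ρ) = (1 + ρ)/2, or 0.65, 0.75, 0.85 and 0.90. At ρ = 0.3 the change test would need about 20/0.65 ≈ 31 per group to match ANCOVA with 20.

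**Step 3: power from the noncentral t, averaged over the slope-estimation factor.**

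| Setting | Test | ρ=0.3 | 0.5 | 0.7 | 0.8 |
|---|---|---|---|---|---|
| d=0.8, k=1 | Change | 54.9% | 69.3% | 88.9% | 97.4% |
| | ANCOVA | 72.2% | 80.1% | 92.5% | 98.1% |
| | Post only | 69.3% | 69.3% | 69.3% | 69.3% |
| d=0.5, k=1 | Change | 25.6% | 33.8% | 51.2% | 68.3% |
| | ANCOVA | 35.7% | 41.9% | 56.7% | 71.6% |
| d=0.8, k=1.25 | Change | 44.9% | 57.6% | 78.1% | 90.8% |
| | ANCOVA | 53.2% | 61.3% | 77.7% | 90.0% |

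Simulation under random assignment (d = 0.8, k = 1) agrees: 54.7 vs 71.9% at ρ = 0.3, and 70.2 vs 80.9% at ρ = 0.5.

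**Step 4: break-even for k = 1.** Setting 1.0278(1 − ρ²) = 2(1 − ρ) gives ρ = 2/1.0278 − 1 = 0.946. With two covariates the factor is 1 + 2/35 = 1.0571, and ρ = 2/1.0571 − 1 = 0.892.

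**Step 5: effect of balancing Level 1 scores.** If a baseline is exactly balanced, the true variance of the change difference falls by the factor (1 + ρ)/2, but the t-test does not know this. Its type I error becomes about 2[1 − Φ(1.96/√((1 + ρ)/2))] = 1.5, 2.4, 3.4 and 3.9%. The documents give no balancing method. Under one assumed method (best of 20 random splits on mean and range of five scores, intercorrelation 0.2, 20,000 trials), the change test gives 2.3, 3.2, 3.7 and 4.1%, and ANCOVA 5.0, 5.2, 4.9 and 4.8%. Power for d = 0.8 is then 56 vs 73, 71 vs 80, 90 vs 93 and 98 vs 98%. Balancing therefore does not lower the change test's power; the gap to ANCOVA remains.

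**Step 6: Levels 2 and 3.** These baselines are not balanced by design. If one differs by 0.3 SD between groups, the change and ANCOVA estimates differ by 0.3(1 − ρ) = 0.21, 0.15, 0.09 and 0.06 SD. Which is closer to the truth depends on how that difference arose.

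**The case against.** **This is a pilot.** The protocol stresses ease of use and compliance and states no power target, so no claim is breached. That is true, and it limits the severity. Efficacy is nevertheless an aim, and formal between-group tests are planned.

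**Only the sample size is documented.** The gap runs from 17 points at ρ = 0.3 to under 1 at ρ = 0.8, and turns slightly negative at k = 1.25 with ρ of 0.7 or more. At d = 0.5 and ρ up to 0.5, neither test reaches 45% power. All of this stands. It argues for presenting the gain as conditional, but the possible loss is about 1 point against a possible gain of 17.

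**Screening on Level 1 deficits (Statistical Plan, Level 1) could narrow the baseline SD.** This stands in part. Suppose the best 20% on a measure are excluded, scores are normal, the effect is 0.8 unselected SD and ρ before selection is 0.3, 0.5 or 0.7. Power is then 62 vs 72, 74 vs 80 and 91 vs 93%. The gain shrinks to about 10, 6 and 2 points but does not reverse. No cut-off is given.

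**The post-only reading is strained.** The sentence refers to pre and post measures, and the Statistical Plan section names no t-test. The post-only losses against ANCOVA (3 to 29 points) are therefore the cost of an ambiguity, not of the plan as most naturally read.

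**Assignment is not stated to be random.** For Levels 2 and 3 this stands. Without as-good-as-random assignment given the Level 1 scores, change and ANCOVA rest on different assumptions and neither is clearly better.

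**Conclusion.** The concern holds. All named group comparisons omit a baseline covariate although the baselines are collected. The planned change test is valid but inefficient, and for Level 1 it is also conservative because the balanced scores are left out of the model.

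The loss matters if ρ is about 0.5 or lower and training does not widen the SD: about 11 to 17 points of power at d = 0.8, and 8 to 10 at d = 0.5. At ρ = 0.7 with equal SDs it is about 4 to 6 points. It is negligible at higher correlation with a large effect, and absent when the post SD is 1.25 times baseline and ρ is 0.7 or more.

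These sizes rest on assumed effect, correlation, SD ratio and significance level. The recommendation is firmest for Level 1. For Levels 2 and 3 it depends on how children are actually assigned. The change should be made, but the trial does not stand or fall by it.

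**What to change.** In the Statistical Plan, name one efficacy test per outcome: the group coefficient at 8 weeks from an ANCOVA on group and that measure's own baseline. For Level 1, a mixed model of the 4- and 8-week values with baseline, group, visit and group-by-visit, testing the 8-week contrast, serves the same aim. Keep the repeated measures ANOVAs and the MANOVA as supportive, and replace the undefined t-test option in the task sections with a reference to this test.

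For Levels 2 and 3, a prespecified summary of the Level 1 scores used in assignment may be added as a covariate; in simulation it changed power by at most 0.4 points. State how children are assigned once the scores are known, so that a reader can judge whether adjustment is justified at those levels.

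The cost is wording only, with no new visits or data. Each outcome loses one degree of freedom, or two with the summary score. With equal SDs that outweighs the gain only above ρ of about 0.95 or 0.89 respectively.
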